5.5 Duration of Therapy

Duration of therapy will depend on individual response, evidence of disease progression and tolerance. In the absence of treatment delays due to adverse event(s), treatment may continue for 2 years or 35 cycles of therapy or until one of the following criteria applies:

- Disease progression in any participant who showed first radiologic evidence of progressive disease (PD) by RECIST 1.1 (see Section 11.1.4) and is deemed clinically stable, it is at the discretion of the investigator to continue treating the participant until progression is confirmed at least 4 weeks from the date of the first radiologic evidence of PD. Further details are described below.
- Intercurrent illness that prevents further administration of treatment
- Unacceptable adverse event(s) which include the following (see also section):
 - Any Grade 2 drug-related uveitis or eye pain or blurred vision that does not respond to topical therapy and does not improve to Grade 1 severity within the re-treatment period OR requires systemic treatment
 - Participants requiring > two dose delays for the same type of event should be removed from protocol
 - Any adverse event, laboratory abnormality, or intercurrent illness which, in the judgment of the investigator, presents a substantial clinical risk to the participant with continued study drug dosing
 - Any dosing interruption lasting >5 weeks, with the following exceptions:
 - Participants being tapered after high dose corticosteroids over one month followed by a two-week observation period will be allowed an additional two weeks to restart treatment (a maximum eight-week interruption).
 - Dosing interruptions >5 weeks that occur for non-drug-related reasons may be allowed if approved by the Investigator. Prior to re-initiating treatment in a participant with a dosing interruption lasting >5 weeks, the PI must be consulted.
 - Grade 2 pneumonitis requiring steroids.
 - Grade 3 or Grade 4 drug-related autoimmune or inflammatory events including uveitis, pneumonitis, diarrhea, colitis, neurologic adverse events, hypersensitivity reaction, or infusion reaction of any duration requires discontinuation except as noted below:
 - Any other grade 3 non-skin, drug-related AE lasting >7 days including fatigue.

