Participants should be off steroids for at least 2 weeks with no recurrence or new events. New immune related events or exacerbation of existing events during steroid treatment or taper suggest the presence of ongoing immune activation and should require permanent discontinuation of pembrolizumab.

Grade 2 events must resolve to grade < 1 or baseline before considering retreatment.

All participants treated with steroids for grade ≥ 2 events should have pembrolizumab held until resolution to grade < 1 for at least 2 weeks following complete removal from steroid treatment except for maintenance replacement doses for adrenal insufficiency (preferably no greater than 10mg prednisone equivalent daily).

All participants treated with steroids for grade ≥ 3 events should have pembrolizumab discontinued. Participants with grade 3 thyroiditis and skin rash may continue therapy as for grade 2 events with resolution and stable replacement treatment.

Participants with hepatitis, pancreatitis, pneumonitis, and colitis are at risk for exacerbation with retreatment if there is residual inflammation and should resolve to Grade 0 or baseline before retreatment. Baseline can mean the initial grade *i.e.* grade ≤ 1 where permitted on study.

Participants with thyroiditis or hypopituitarism who are stable as above may be restarted with replacement hormones including thyroid hormone and physiologic doses only of corticosteroids. Please note that hypophysitis with symptoms of headache, visual or neurologic changes or radiologic evidence of pituitary enlargement and other CNS events such as aseptic meningitis or encephalitis should be considered grade 3 events.

Prior to starting corticosteroids or hormone replacement for any reason, appropriate endocrine testing including cortisol, ACTH, TSH and T4 must be drawn if clinically feasible to document baseline function and distinguish the pituitary from peripheral organ dysfunction and later from steroid (or thyroid) treatment associated ACTH (or TSH) suppression. Steroids should be started prior to obtaining results based on clinical indications.

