6. DOSING DELAYS/DOSE MODIFICATIONS

Dose delays and modifications will be made as indicated in the following table(s). The descriptions and grading scales found in the revised NCI Common Terminology Criteria for Adverse Events (CTCAE) version 5.0 will be utilized for dose delays and dose modifications. A copy of the CTCAE version 5.0 can be downloaded from the CTEP website http://ctep.cancer.gov/protocolDevelopment/electronic_applications/ctc.htm.

Dosing interruptions are permitted in the case of medical / surgical events or logistical reasons not related to study therapy (e.g., elective surgery, unrelated medical events, participant vacation, and/or holidays). Participants should be placed back on study therapy within 5 weeks of the scheduled interruption, unless otherwise discussed with the Sponsor. The reason for interruption should be documented in the participant's study record.

Dose modifications and delays for eribulin will be allowed and are described below. No re-escalation will be allowed for eribulin. Dose delays for pembrolizumab for adverse events are described below. There are no dose reductions of pembrolizumab allowed. See Section 5.9 for guidelines regarding resumption of pembrolizumab following dose delays.

For toxicities in this Section which are attributable to pembrolizumab alone, only pembrolizumab should be held as directed. It is permissible to continue eribulin despite discontinuation of pembrolizumab in these select cases. This will be left to the treating physician's discretion after discussion and approval of the study PI.

For toxicities in this Section which are attributable to eribulin alone, only eribulin should be held

as directed. It is permissible to continue pembrolizumab despite discontinuation of eribulin in these select cases. This will be left to the treating physician's discretion after discussion and approval by the study PI.

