General instructions: 
 1. Corticosteroid taper should be initiated upon AE improving to Grade 1 or less and continue to taper over at least 4 weeks. 2. For situations where pembrolizumab has been withheld, pembrolizumab can be resumed after AE has been reduced to Grade 1 or 0 and corticosteroid has been tapered. Pembrolizumab should be permanently discontinued if AE does not resolve within 12 weeks of last dose or corticosteroids cannot be reduced to ≤ 10 mg prednisone or equivalent per day within 12 weeks. 3. For severe and life-threatening irAEs, IV corticosteroid should be initiated first followed by oral steroid. Other immunosuppressive treatment should be initiated if irAEs cannot be controlled by corticosteroids. 				
Immune-related AEs	Toxicity grade or conditions (CTCAEv5.0)	Action taken to pembrolizumab	irAE management with corticosteroid and/or other therapies	Monitor and follow-up
Pneumonitis	Grade 2	Withhold	
 • Administer corticosteroids (initial dose of 1-2 mg/kg prednisone or equivalent) followed by taper 	
 • Monitor participants for signs and symptoms of pneumonitis • Evaluate participants with suspected pneumonitis with radiographic imaging and initiate corticosteroid treatment • Add prophylactic antibiotics for opportunistic infections
	Grade 3 or 4, or recurrent Grade 2	Permanently discontinue		
Diarrhea / Colitis	Grade 2 or 3	Withhold	
 • Administer corticosteroids (initial dose of 1-2 mg/kg prednisone or equivalent) followed by taper 	
 • Monitor participants for signs and symptoms of enterocolitis (ie, diarrhea, abdominal pain, blood or mucus in stool with or without fever) and of bowel perforation (ie, peritoneal signs and ileus). • Participants with \geq Grade 2 diarrhea suspecting colitis should consider GI consultation and performing endoscopy to rule out colitis. • Participants with diarrhea/colitis should be advised to drink liberal quantities of clear fluids. If sufficient oral fluid intake is not feasible, fluid and electrolytes should be substituted via IV infusion.
	Grade 4	Permanently discontinue		

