Grade 2	Continue at investigator discretion
Grade 3	Hold until ≤ Grade 1. Resume at same dose level at investigator discretion.
Grade 4	Stop pembrolizumab
Participants with fever should be evaluated as clinically appropriate. Participants may experience isolated fever during infusion reactions or up to several days after infusion. Evaluation over the course of 1-2 weeks should be done for other autoimmune events that may present as fever	
See section 5.10: Treatment of Pembrolizumab Infusion reactions	

If treatment is delayed >8 weeks for an adverse event, the participant must be permanently discontinued from study therapy.

Participants requiring high dose steroid treatment for autoimmune or inflammatory events should be managed as described in section 5.9, except for a short course of tapering steroids for infusion reaction, skin rash, or endocrine events.

Participants with grade 3 thyroiditis and skin rash may continue therapy as for grade 2 events with resolution and stable replacement treatment.

Participants with thyroiditis or hypopituitarism who are stable as above may be restarted with replacement hormones including thyroid hormone and physiologic doses of corticosteroids. Please note that grade for hypophysitis with symptoms of headache, visual, or neurologic changes or radiologic evidence of pituitary enlargement and other CNS events such as aseptic meningitis or encephalitis should be considered grade 3 events.

Any participant who requires additional immune suppressive treatment beyond steroids should stop pembrolizumab.

Participants requiring > two dose delays, other than for evaluation for the same event, should stop pembrolizumab. Participants may be dose-delayed for evaluation and restarted depending on results.

Prior to starting corticosteroids or hormone replacement for any reason, appropriate endocrine testing including cortisol, ACTH, TSH and T4 must be obtained to document baseline.

Please note that in some cases the treatment algorithms recommend steroids if symptoms do not resolve in 7 days. However, this recommendation is not meant to delay steroid treatment at any time it is clinically indicated.

Any participant started on corticosteroids initially who is determined to not require steroids treatment for an autoimmune adverse event may resume therapy after a 2-week observation period without further symptoms at the discretion of the PI or investigator.

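### Table 4.1 permits pembrolizumab restart at a residual grade and without the steroid-free interval that Section 5.8 asks for, and Section 6 points to the wrong section for the restart criteria

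*Combined protocol and SAP*

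**What the plan says.** Table 4.1 (Section 6.2) opens with general instructions. Instruction 1 sets the taper: "Corticosteroid taper should be initiated upon AE improving to Grade 1 or less and continue to taper over at least 4 weeks". Instruction 2 sets the restart: "pembrolizumab can be resumed after AE has been reduced to Grade 1 or 0 and corticosteroid has been tapered". It makes no organ exception and names no steroid-free interval.

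Section 5.8, which holds the criteria for resuming after an immune-related event, says of hepatitis, pancreatitis, pneumonitis and colitis that participants "are at risk for exacerbation with retreatment if there is residual inflammation and should resolve to Grade 0 or baseline before retreatment". For those given corticosteroids it adds: "Participants should be off steroids for at least 2 weeks with no recurrence or new events". For steroid-treated events of Grade 2 or higher, the hold runs "for at least 2 weeks following complete removal from steroid treatment except for maintenance replacement doses for adrenal insufficiency".

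Two other places also use a two-week interval. Section 5.5 describes a high-dose steroid taper "over one month followed by a two-week observation period will be allowed an additional two weeks to restart treatment". Section 6.2, after Table 4.9, says that a participant who turned out not to need steroids "may resume therapy after a 2-week observation period without further symptoms at the discretion of the PI or investigator".

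The opening text of Section 6 tells the reader: "See Section 5.9 for guidelines regarding resumption of pembrolizumab following dose delays". Section 5.9 covers infusion reactions.

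**The concern.** The table that a site is most likely to use when managing an event permits re-dosing in a state that 5.8 describes as carrying a risk of exacerbation. The protocol does not say which text governs, and the references that should lead from Section 6 to 5.8 lead elsewhere. At stake is re-exposure to pembrolizumab with residual Grade 1 inflammation directly after a taper, and inconsistent judgement of what counts as a deviation. This is a matter of safety and conduct. It does not touch the primary endpoint, the sample size or the decision rule.

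**Working it through.** No statistical figure is involved, so the check is a comparison of texts followed by simple timing.

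**Restart conditions side by side**

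| Text | Grade needed | Steroid condition |
|---|---|---|
| Table 4.1, instruction 2 | 1 or 0, all organs | tapered; no interval off steroids |
| 5.8 | 0 or baseline for the four named events | off for at least 2 weeks |
| 5.5 | none stated | one-month taper, then two weeks of observation |
| 6.2, after Table 4.9 | no further symptoms | two weeks of observation even if steroids were not needed |
| 5.2.3 (Day 1 of later cycles) | baseline or below Grade 2 | none stated |
| Appendix B, Grade 2 colitis | 1 | if steroids used, taper of at least a month; no interval |
| Appendix B, Grade 2 hepatic, steroid branch | 1 or baseline | taper of at least a month; no interval |

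**Test case.** A participant enters at Grade 0, develops Grade 2 colitis, receives steroids, improves to Grade 1 and has just finished the taper. Table 4.1 permits restart. Section 5.8 does not, on two counts: Grade 1 is neither Grade 0 nor this participant's baseline, and the two weeks off steroids have not passed. For a participant who entered at Grade 1, baseline in 5.8 can mean that entry grade, so only the two-week conflict remains.

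**Pointers.** Three references in Section 6 name 5.9 where 5.8 is meant: the opening text of Section 6, the opening of 6.2, and the high-dose steroid sentence after Table 4.9. A fourth, at the foot of Table 4.9, names 5.10 for infusion reactions; 5.10 is Treatment Beyond Progression and the right section is 5.9. The reference to 5.9 in 5.3.2 is correct.

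**Minimum time from Grade 1 to restart.** Section 5.8 gives no taper length, so the 4 weeks in Table 4.1 are used for both.
- Table 4.1: 4 weeks.
- Section 5.8: 4 + 2 = 6 weeks, with Grade 0 or baseline also required for the four events.

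**Effect of the 21-day cycle.** Suppose eribulin continues on schedule and pembrolizumab can rejoin only on Day 1, at weeks 0, 3, 6, 9. Let Grade 1 be reached t weeks after a Day 1. Restart falls on the first Day 1 at or after t + 4 (Table 4.1) or t + 6 (5.8).
- t = 0: 4 and 6 both give week 6; difference nil.
- t = 1: 5 gives week 6, 7 gives week 9; difference 3 weeks.
- t = 2.5: 6.5 and 8.5 both give week 9; difference nil.

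**Scale.** Section 2.6 puts possible immune-related colitis, all grades, below 4% in the breast cancer trial of this combination. If that carried over, 0.04 × 57 = 2.28, so fewer than 2.3 participants. This covers colitis only. Pneumonitis was 11.2%, or 0.112 × 57 = 6.4 participants at any grade, but 5.5 lists steroid-requiring Grade 2 pneumonitis among the reasons to stop therapy. The documents give no immune hepatitis rate and no share left at Grade 1 after a taper.

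**The case against.** The best defence is that the texts can be read together. Table 4.1 gives a general, permissive instruction; 5.8 is titled as the restart criteria, is organ-specific and gives reasons; and anyone who follows 5.8 also satisfies the table. The faulty references describe their target in words, and the right section is the one just before 5.9. That reading is plausible, but no sentence states it, and a site that follows the numbers as printed will not find 5.8.

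A second objection concerns the grade. Section 5.2.3 and Appendix B agree with Table 4.1 that Grade 1 is enough, so on grade 5.8 is the stricter exception. This stands. Only the two-week interval has support outside 5.8. Appendix B does say to resume per protocol, but that returns the reader to the same conflict.

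A third objection is that a blanket instruction to follow 5.8 for every restart would do too much, and this also stands. It would carry the below-Grade-1 wording of 5.8 to all steroid-treated events of Grade 2 or higher, against Table 4.3, which allows rash to restart at Grade 1. It would move steroid-treated Grade 3 colitis from withhold to discontinue while the Table 4.1 row still said withhold. It would also set the 8-week resolution limit of 5.8 for high-dose steroid cases beside the 12-week limit in instruction 2. The change should be narrower.

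**Conclusion.** The conflict is real and confined to two conditions: the restart grade for four named organ events in participants who entered below the residual grade, and the two weeks off steroids after steroid treatment. The minimum times differ by about 2 weeks (4 against 6), assuming the same 4-week taper.

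Four stronger readings are not supported:
- A reader might infer that the table always brings restart forward by two weeks. With Day 1 dosing every 21 days the actual difference depends on timing and may be nil.
- A reader might compare the time left under the eight-week cap in 5.5 for each rule. Table 4.1 carries its own 12-week limit, so that comparison mixes two texts.
- A reader might conclude that Table 4.1 is the sole outlier. On grade it is not.
- A reader might expect an effect on the results. No endpoint or statistical figure changes, and the documents allow no count of affected participants beyond the view that they are likely to be few.

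Following 5.8 on grade is therefore a judgement. It rests on 5.8 being the specific text and the one that gives a safety reason. Severity is minor to moderate. If no participant is still on treatment, which the documents do not state, the value lies in judging deviations and in any reuse of this text.

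**What to change.** 1. In Table 4.1, instruction 2, add after the first sentence: *After steroid treatment, do not resume pembrolizumab until at least 2 weeks after steroids have been stopped completely (replacement doses excepted); colitis, hepatitis, pneumonitis and pancreatitis must be at Grade 0 or baseline (Section 5.8).* Keep the endocrinopathy note and leave the withhold and discontinue rows unchanged. Section 6.2, after Table 4.9, excepts short tapering courses for infusion reaction, rash and endocrine events; that exception should stand.
2. Change 5.9 to 5.8 in the opening text of Section 6, the opening of 6.2 and the high-dose steroid sentence after Table 4.9. Change 5.10 to 5.9 at the foot of Table 4.9. Leave 5.3.2 as it is.
3. In the Appendix B rows for Grade 2 colitis and Grade 2 hepatic events, replace the instruction to resume per protocol with *resume per Section 5.8*.

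The cost is one sentence, four section numbers and two table rows, with no added visits, procedures or participants. Some participants will restart pembrolizumab later, or not at all if they stay at Grade 1 above a Grade 0 baseline or exceed the permitted interruption. Section 5.8 lets eribulin continue meanwhile.

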5.8 Criteria to Resume Treatment after a pembrolizumab related iAE

Management of adverse events is summarized in section 6 and may include holding of pembrolizumab, and/or the use of steroids for the management of immune related AEs. If pembrolizumab is held for toxicity, participants are permitted to continue protocol therapy with eribulin. Eribulin can be continued during corticosteroid treatment.

If drug administration is held until the next scheduled time point, please continue to count weeks/doses. If participants must be delayed due to toxicity, all assessments can be obtained with the modified treatment dose schedule as noted in this section.

Pembrolizumab may be interrupted for situations other than treatment-related AEs such as medical / surgical events or logistical reasons not related to study therapy. Participants should be placed back on study therapy within 8 weeks of the scheduled interruption, unless otherwise discussed with the Sponsor. The reason for interruption should be documented in the participant's study record.

Restarting pembrolizumab may be considered in participants who experience grade 2 events and some grade 3 events (skin rash and thyroiditis). Because of this, stopping treatment and starting steroids earlier, as per section 6, to obtain resolution with the possibility for restarting rather than waiting for higher grade events is encouraged.

For non-autoimmune or non-inflammatory events, participants may resume treatment with study drug when the drug-related AE(s) resolves to Grade ≤ 1 or the baseline value, with the following exceptions:

- Evaluation to exclude any additional immune mediated events (endocrine, GI, and liver / pancreas function) as clinically indicated must be made prior to restarting. [SEP]
- Non-drug-related toxicity including hepatic, pulmonary toxicity, diarrhea, or colitis, must have resolved to baseline before treatment is resumed. [SEP] If the criteria to resume treatment are met, the participant should restart treatment no sooner than the next scheduled time point per protocol. However, if the treatment is delayed past the next scheduled time point per protocol, the treatment should resume at the earliest convenient point [SEP] that is within the five-week delay period.

For participants treated with corticosteroids:

For participants treated with high dose steroids with pembrolizumab, toxicity must resolve to baseline within 8 weeks of treatment.

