All other immune-related AEs	Intolerable/persistent Grade 2	Withhold	
 Based on type and severity of AE administer corticosteroids 	
 Ensure adequate evaluation to confirm etiology and/or exclude other causes
	Grade 3	Withhold or discontinue based on the type of event. Events that require discontinuation include and not limited to: Guillain-Barre Syndrome, encephalitis		

	Grade 4 or recurrent Grade 3	Permanently discontinue		
1. Withhold or permanently discontinue pembrolizumab is at the discretion of the investigator or treating physician. NOTE: For participants with Grade 3 or 4 immune-related endocrinopathy where withhold of pembrolizumab is required, pembrolizumab may be resumed when AE resolves to \leq Grade 2 and is controlled with hormonal replacement therapy or achieved metabolic control (in case of T1DM).				

Table 4.2 Pembrolizumab dose delay for non-immunologically mediated adverse events

ALL OTHER EVENTS*	Management/Next Dose for Pembrolizumab
\leq Grade 1	No change in dose
Grade 2	Hold until \leq Grade 1 OR baseline (exceptions as noted below); Evaluate and continue at investigator discretion
Grade 3	Stop pembrolizumab (exceptions as noted below)
Grade 4	Stop pembrolizumab
*Not Pembrolizumab related, or pembrolizumab related non-immunologically mediated Recommended management: As clinically indicated	

- Any grade 2 drug-related uveitis or eye pain or blurred vision that does not respond to topical therapy and does not improve to Grade 1 severity within the re-treatment period OR requires systemic treatment should result in protocol treatment discontinuation.
- Any adverse event, laboratory abnormality, or intercurrent illness which, in the judgment of the investigator, presents a substantial clinical risk to the participant with continued study drug dosing should result in protocol treatment discontinuation.
- Tumor pain or associated tumor flare does not require permanent discontinuation.
- Participants with any grade < 2 laboratory abnormality may continue study treatment at the discretion^[SEP] of the investigator. Any grade 3 or 4 drug-related laboratory abnormality or electrolyte abnormality, that can be managed independently from underlying organ pathology with electrolyte replacement, hormone replacement, insulin, or that does not require treatment **does not** require discontinuation.

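### Table 4.2 stops pembrolizumab at Grade 3 even for events unrelated to it, while Sections 6 and 5.8 tell the investigator to hold only eribulin, interrupt, or resume

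*Combined protocol and SAP*

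**What the plan says.** Table 4.2 (Section 6.2) is the residual table for pembrolizumab. Its footnote gives the scope as "Not Pembrolizumab related, or pembrolizumab related non-immunologically mediated". At Grade 2 pembrolizumab is held, after which the instruction is "Evaluate and continue at investigator discretion". The Grade 3 row reads "Stop pembrolizumab (exceptions as noted below").

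The list beneath the table gives three exceptions that bear on Grade 3:
- tumor pain: "Tumor pain or associated tumor flare does not require permanent discontinuation";
- laboratory values: "Any grade 3 or 4 drug-related laboratory abnormality or electrolyte abnormality, that can be managed independently from underlying organ pathology with electrolyte replacement", extended to hormone replacement, insulin or no treatment at all;
- expected hematologic events related to eribulin, which follow the eribulin tables and need no pembrolizumab delay.

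Other passages address the same events:
- Section 6, introduction: "For toxicities in this Section which are attributable to eribulin alone, only eribulin should be held". Pembrolizumab may then continue with the approval of the study PI. The same introduction allows dosing to be interrupted for medical or surgical events unrelated to study therapy, with a return to treatment.
- Section 5.8: "For non-autoimmune or non-inflammatory events, participants may resume treatment with study drug when the drug-related AE(s) resolves to Grade" 1 or lower, or to baseline. Toxicity not related to study drug has to be back at baseline before treatment restarts.
- Section 5.5 lists, among the reasons for leaving protocol therapy: "Any other grade 3 non-skin, drug-related AE lasting >7 days including fatigue".

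**The concern.** Table 4.2 distinguishes hold (Grade 2) from stop (Grade 3), so its Grade 3 row cannot be read as a temporary hold. Because the footnote brings in events that pembrolizumab did not cause, the stop applies to them too, and that is where Sections 6 and 5.8 say otherwise.

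What is at stake is exposure to one half of the combination, and consistency between investigators. Section 5.3.4 allows eribulin to continue alone once pembrolizumab is stopped for toxicity, and Section 13.9.2 analyses everyone by intent to treat. A participant who lost pembrolizumab early but was progression-free at 12 weeks would count as a success for the combination. Sections 2.4 and 2.7 set the design targets out of concern that a 40% rate might come from the single agents. The protocol therefore has its own reason to want pembrolizumab exposure settled by one rule. The conflict also leaves it unclear which action is a protocol deviation.

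**Working it through.** There is no figure in the plan to reproduce. The check is a comparison of texts, followed by one small calculation of exposure.

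**Step 1: which events remain under the Grade 3 stop.** Take out the three exceptions above. Take out events with their own pembrolizumab rule: immune-related events (Table 4.1), rash and oral lesions (4.3), pancreatitis or amylase/lipase (4.4), nausea and vomiting (4.5), fatigue (4.6), neurologic events (4.7), infusion reactions (4.8) and fever (4.9). Still inside Table 4.2 are, for example, infection, abdominal pain, and diarrhea judged non-immune and due to eribulin. These are not hypothetical: Section 7.1.1.2 lists Grade 3 to 4 urinary tract infection (2.2%) and abdominal pain (1.8%) for eribulin.

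**Step 2: the passages applied to the same event.**

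- *Grade 3 diarrhea, non-immune, attributed to eribulin alone, recovering in 3 days.* Table 4.2: stop pembrolizumab. Section 6: hold eribulin only; pembrolizumab may continue with PI approval. Table 3.1: hold eribulin. Section 5.8: may resume on recovery. Section 5.5: the 7-day condition is not met.
- *Grade 3 infection related to neither drug.* Table 4.2: stop pembrolizumab. Section 6: interrupt and return. Section 5.8: resume at baseline. Section 5.5: the residual Grade 3 criterion does not apply, since it is limited to drug-related events.

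In both cases the instructions cannot all be followed.

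**Step 3: do the exceptions already resolve it?** One exception is written specifically for eribulin-related events, and only for expected hematologic ones. If the Section 6 attribution rule already overrode Table 4.2, that exception would be unnecessary. Its presence suggests that other eribulin-related Grade 3 events stay under the stop.

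**Step 4: a comparison between tables.** Table 4.1 withholds pembrolizumab for immune-related Grade 3 diarrhea or colitis; Table 4.2 stops it for non-immune Grade 3 diarrhea. Taken literally, the two tables are stricter with an event that pembrolizumab did not cause. This holds between the tables only: for immune-related Grade 3 diarrhea, Section 5.5 and the gastrointestinal algorithm in Appendix B direct discontinuation.

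**Step 5: exposure before the primary assessment.** Twelve weeks is 12 × 7 / 21 = 4 cycles, so at most 4 pembrolizumab doses (Day 1 of cycles 1 to 4) are scheduled before week 12. For an event in cycle 1, Table 4.2 leaves 1 dose of 4. The Section 6 rule for eribulin-only toxicity leaves up to 4 of 4.

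**The case against.** The best defence is that Section 6 introduces the whole dose-modification section, speaks directly to eribulin-only toxicity and requires PI approval, so it could be taken to govern the tables under it. Section 6.2 also presents the tables as guidelines, and the Table 4.2 footnote leaves management to clinical judgement. This is a possible reading, but nothing states that the introduction prevails over an explicit stop row, and the hematologic-only exception argues against it. For events related to neither drug, the footnote's scope is explicit.

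Section 5.8 is not clean support. Its heading concerns immune events caused by pembrolizumab, and one sentence there speaks of restarting after Grade 2 and some Grade 3 events, naming skin rash and thyroiditis. That fits a Grade 3 stop elsewhere. Its provisions for non-immune and non-drug-related events carry no grade ceiling, so 5.8 is itself unclear rather than in agreement with Table 4.2. This part of the objection stands as a limit.

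Section 5.5 might be read as a direct contradiction, because it requires relatedness and more than 7 days where Table 4.2 requires neither. But it governs removal from all protocol therapy, whereas Table 4.2 concerns one drug. Stopping one drug on a broader trigger than full removal is not contradictory in itself. It is at most a secondary difference.

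A reader might also infer that ordinary eribulin nausea stops pembrolizumab. It does not fall under Table 4.2: Table 4.5 holds at Grade 3 and stops only if symptoms have not resolved within 7 days of symptomatic treatment.

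**Conclusion.** The contradiction is real and confined to Grade 3 events that have no table of their own and no listed exception, where the event is unrelated to pembrolizumab or attributed to eribulin alone. For these, Table 4.2 conflicts with Section 6, and with two provisions of Section 5.8 that are themselves qualified by a third. It is an internal inconsistency, worth correcting because it determines exposure to a study drug.

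Its size in participants is unknown. A reader might try to derive a minimum from the breast cancer combination trial in Section 2.6: 47.7% with Grade 3 related events less 30.8% with Grade 3 or 4 neutropenia leaves 16.9%, or 0.169 × 19 = 3.2 participants per arm. The documents do not support that as a floor. The subtraction mixes grade bands. The other leading Grade 3 or 4 events there, neuropathy, anemia, fatigue and hypokalemia, sum to 9.3 + 5.6 + 5.6 + 5.6 = 26.1%, and these have their own tables or may meet an exception. Grade 3 or 4 immune-related events (18.7%) lie outside Table 4.2 by its title. Either group could absorb the whole 16.9%, so these figures are compatible with a floor of zero. Nor does Section 2.6 limit the rates to the first 12 weeks.

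A reader might further infer that the week-12 result is materially distorted. That is not shown. Continuing on one agent is expressly permitted, stopping pembrolizumab is not in itself a failure under Section 13.1, and no figure gives the frequency or direction of an effect. With 19 participants per arm and a threshold of 9, one or two participants handled differently could matter in a borderline arm, but only if their week-12 status changed.

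**What to change.** Reconcile Table 4.2, including its footnote and exception list, with the Section 6 introduction and Section 5.8, so that one rule states what happens to pembrolizumab after a Grade 3 event that is (a) unrelated to it or (b) attributable to eribulin alone. State which text prevails where a table and the introduction differ. Within Section 5.8, reconcile the restart sentence with the provisions for non-immune and non-drug-related events. Check the Section 5.5 Grade 3 criterion, and the Table 4.1 entry for Grade 3 diarrhea, against the result. Which rule to adopt is a clinical decision for the sponsor and is not proposed here.

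The cost is protocol wording. Sample size, endpoint and decision rule do not change.
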